3 STUDY TREATMENTS

3.1 INVESTIGATIONAL TREATMENT

The iLux procedure shall be performed on both eyes on the same day.

- 1. Eye makeup shall be removed.
- 2. Contact lens (if wearing) shall be removed.
- 3. The iLux device shall be prepared for use in accordance with the iLux User Manual,

6. iLux inner eyelid pad on the iLux Disposable shall be positioned: a) behind the lower eyelid in the central-temporal zone in the first treatment, b) behind the lower eyelid in the central-nasal position in the second treatment, c) behind the upper eyelid in the central-temporal zone in the third treatment, d) behind the upper eyelid in the central-nasal position in the fourth treatment. In all cases, the inner eyelid pad shall be positioned such that the support arms of the iLux Disposable are touching the eye lid margin.

7. The iLux outer eyelid pad on the iLux Disposable shall be advanced using the Compression Control button to cause this outer eyelid pad to apply pressure against the outer eyelid. The compression applied to the Compression Control button will be recorded using an external force sensor.

8. The iLux light/heat shall be activated by sliding the light/heat switch forward,

9. Within ten seconds after the fourth warming cycle,
camera will be used to measure the temperature of the cornea and surrounding eye tissue. Subjects shall be asked to close their eyes for five seconds, then hold them open while

3.2 POST-TREATMENT DETAILS:

Post-procedure, the subject shall report any discomfort to the study site.

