5.4.2 Anticipated Adverse Events

- Eyelid/eye Pain
- Eyelid Irritation or Inflammation
- Ocular Surface Irritation or Inflammation
- Ocular Symptoms Burning, stinging, tearing, itching, discharge, redness, foreign body sensation, visual disturbance, sensitivity to light.

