Appendix 2: Case Report Forms

SUBJECT 1	ID:	-	

FORM 1: INCLUSION/EXCLUSION - Page 1 of 1

Screening/Pre-Treatment Date (DD-MMM-YYYY)	
Did subject meet all inclusion and no exclusion criteria? If no, indicate which criteria the subject did not meet:	☐ Yes ☐ No
Inclusion criterion #/criteria #s not met:	
Exclusion criterion #/criteria #s not met:	
Was Sponsor notified of protocol deviation?	☐ Yes ☐ No ☐ N/A
Was IRB notified of protocol deviation?	☐ Yes ☐ No ☐ N/A
Did subject sign an informed consent form?	☐ Yes ☐ No
If "Yes", please provide date signed (DD-MMM-YYYY)	

Subject Assessment Schedule:

ASSESSMENT	PRE- TREATMENT	TREATMENT	POST- TREATMENT	FOLLOW UP
Treatment Window	Day 0	Day 0	Day 0	Day 1 (-0/+3 days)
Informed Consent	X			
Demographics/medical/ocular history	X			
Visual Acuity	X		X	
Slit Lamp for Anterior Segment health	X		X	
Lid Margin Abnormalities	X		X	
Corneal fluorescein staining slit lamp evaluation	X		X	
Intraocular pressure	X		X	
Cornea and surrounding eye tissue temperature	X		X	
iLux heating		X		
Discomfort/pain questionnaire	X		X	X
Adverse Events		X	X	X

Required Case Report Forms by Assessment:

Pre-Treatment	Forms 1-5	
Treatment	Forms 6-7	Form 8 with any Adverse Event Form 9 with Device Event
Post-Treatment	Forms 4-5	Form 8 with any Adverse Event
Follow-Up	Form 5	Form 8 with any Adverse Event

SUBJECT ID:	_

FORM 2: DEMOGRAPHICS & MEDICAL HISTORY- Page 1 of 1

Demographics:				
Date of birth (DD-MMM-YY Gender Ethnicity Race	□ Male □ Femal□ Hispanic or Lat□ American India	ino 🛭 Not Hispan	🗖 Asian 🗖 Black or African An	nerican
Medical History Does the subject have: Diabetes? Hypertension? Hypercholesterolemia? Allergies to medication? Infection disease (HIV, TB)?		# of Years	Treated w/ Medication? Yes No	
List all medications subject is	-	, please specify:	opathic, birth control, or remedies	
List all major injuries, surgeri	es, and/or hospitaliz	ations subject has	had:	
Does the subject drive? Does the subject have difficult	ty driving?	☐ Yes ☐ No ☐ Yes ☐ No		
If Yes, please explain: Does the subject use tobacco Does the subject use alcohol p Does the subject use illicit dru	products?	Yes No Yes No Yes No		
PCP Name:				
PCP Phone #:				
Last Medical Exam Is the subject currently under If yes, please specify:	- medical care for any	- v condition?	(DD-MMM-YYYY) ☐ Yes ☐ No	

SUBJECT ID:	_
-------------	---

FORM 3: SYMPTOMS & OCULAR HISTORY- Page 1 of 1

Subject General Symptoms		Subject Ocular Symp	toms	Which Eye?

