Constitutional: Fever, Weight Loss, Appetite	☐ Yes ☐ No	Sudden Vision Loss	☐ Yes ☐ No	□ OD □ OS
Integumentary: Skin conditions/ disorders	☐ Yes ☐ No	Blurred Vision	☐ Yes ☐ No	OD OS
Neurological: Headaches, Migraine, Seizures	☐ Yes ☐ No	Loss of Side Vision	☐ Yes ☐ No	□ OD □ OS
Ear, Nose, Throat: Allergies, Sinus, Cough,	☐ Yes ☐ No	Double Vision	☐ Yes ☐ No	□ OD □ OS
Dry Throat/Mouth		Floaters	☐ Yes ☐ No	□ OD □ OS
Respiratory: Asthma, Emphysema, Bronchitis	☐ Yes ☐ No	Flashes	☐ Yes ☐ No	□ OD □ OS
Vascular: Hypertension, Stroke, Heart Pain	☐ Yes ☐ No	Mucus Discharge	☐ Yes ☐ No	□ OD □ OS
Gastrointestinal: Diarrhea, Constipation	☐ Yes ☐ No	Redness	☐ Yes ☐ No	□ OD □ OS
Genitourinary: Genitals, Kidneys, Bladder	☐ Yes ☐ No	Gritty Feeling	☐ Yes ☐ No	□ OD □ OS
Bones/ Joints: Rheumat Arthritis, Muscle Pain	☐ Yes ☐ No	Itchy/Burning	☐ Yes ☐ No	□ OD □ OS
Lymphatic/Hematologic : Anemia, Bleeding	☐ Yes ☐ No	Tearing/Watery	☐ Yes ☐ No	□ OD □ OS
Allergic Immunologic: Allergies, Immune	☐ Yes ☐ No	Glare	☐ Yes ☐ No	□ OD □ OS
Psychiatric: Depression/Anxiety	☐ Yes ☐ No	Eye Pain/Discomfort	☐ Yes ☐ No	□ OD □ OS
		Haloes at Night	☐ Yes ☐ No	□ OD □ OS
Family Medical and Ocular History		Relative/Relationship	):	
DE 1				
Blindness	☐ Yes ☐ No			
Cataracts	☐ Yes ☐ No			
Cataracts	a 163 a 110			
Glaucoma	☐ Yes ☐ No			
Macular Degeneration	☐ Yes ☐ No			
Retinal Disease	☐ Yes ☐ No			
Arthritis	☐ Yes ☐ No			
Company	D Ves D Ne			
Cancer	☐ Yes ☐ No			
Diabetes	☐ Yes ☐ No			
Diabetes	a res a no			
Hypertension	☐ Yes ☐ No			
Trypercension	— 165 — 110			
Heart Disease	☐ Yes ☐ No			
	_ 100 _ 110			
Kidney Disease	☐ Yes ☐ No			
22.02.07	_ 133 _113			
Thyroid Disease	☐ Yes ☐ No			
•				
Other:	☐ Yes ☐ No			
Dlagg gracify				
Please specify:				

SUBJECT	ID:	-

[figure not shown]
FORM 4: OCULAR ASSESSMENT - Page 1 of 2					
Assessment Timeframe					
Visual Acuity	Total ETDRS	Letters Read			
Uncorrected	OD	os	OD ☐ Finger Count OR ☐ Hand Movement ☐ Light Perception	OS ☐ Finger Count ☐ Hand Movement ☐ Light Perception	
Habitual correction Best correction			OR Hand Movement Light Perception Finger Count OR Hand Movement Light Perception Light Perception	☐ Finger Count ☐ Hand Movement ☐ Light Perception ☐ Finger Count ☐ Hand Movement ☐ Light Perception	
Slit Lamp Examination		A . 7. I. A .			
0 = No Clinical Finding; 1 =	: Non-Clinically Signi OD	ficant Finding; 2 = A OS	lbnormal Finding; if > 0, p l OD	lease specify below : OS	

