Adnexa	0 0 1 0 2	0 0 1 0 2		_	
Conjunctiva	0 0 1 0 2	0 0 1 2			
Sclera	0 0 1 0 2	0 1 2			
Corneal clarity	0 1 2	0 0 1 0 2			
Tear film	0 0 1 0 2	0 0 1 0 2			
Anterior chamber	0 0 1 0 2	0 0 1 0 2			
Iris	0 1 2	0 1 2			
Intraocular Pressure	OD	os			
Goldmann (mmHg)			_		
Lid Margin Assessment	C	heck "Yes" for each c	condition that applies to each	ı lid	
		er Lid		ver Lid	
0=None 1=Irregular Lid Margin 2=Vascular Engorgement 3=Ant/Post Replacement of	OD Yes No Yes No Yes No	OS Yes No Yes No Yes No	OD Yes No Yes No Yes No	OS ☐ Yes ☐ No ☐ Yes ☐ No ☐ Yes ☐ No	
Mucocutaneous Junction	☐ Yes ☐ No	☐ Yes ☐ No	☐ Yes ☐ No	☐ Yes ☐ No	

[figure not shown]

FORM 4: OCULAR ASSESSMENT - Page 2 of 2

Corneal Fluorescein Staining Grading

Enter the staining grade for each segment of each eye

0 = Normal; No staining

1 = Mild; Superficial staining, micropunctate staining

2 = Moderate; Macropunctate staining with some coalescent areas

3 = Severe; Numerous macropunctate areas and/or patches

Manifest Refraction	+/-	Sphere	Cylinder	Axis
OD				X
OS			-	X
Keratotomy	OD			OS
Steep	D	0		D0
Flat	D	0		D0
Eve Temperature Assessment		OD	OS	
1st Reading - Pre-Treatment and Post-	-Treatment			
Corneal Temp (close eye for 5 sec, the	n open)			_
Surrounding Tissue Temp (close eye for	or 5 sec)			
2nd Reading - Post-Treatment Only	_			
Corneal Temp (close eye for 5 sec, the	n open)			_
Surrounding Tissue Temp (close eye f	or 5 sec)			
3rd Reading- Post-Treatment Only				_
Corneal Temp (close eye for 5 sec, the	n open)			_
Surrounding Tissue Temp (close eye for	or 5 sec)			_

FORM 5: PAIN/DISCOMFORT ASSESSMENT- Page 1 of 1

Assessment Date (DD-MMM-YYYY)				
Assessment Timeframe	☐ Pre-Treatment ☐ Post-Treatment ☐ Follow-Up			
Assessment Intertaine	☐ Other, please specify:			
	OD	os		
Subject's pain level (scale 0-10)				

Score	Level of Discomfort/Pain	Description to Anchor Subjective Response	
0	No discomfort or pain	Minimal recognition of pressure only. Equal to the touch of a finger on the skin. Awareness but no discomfort.	
2	Slight or transient awareness of pressure without pain	Pressure tolerable and could be endured indefinitely without compromise to daily activities. Examples: bruise; medical injection; wearing dress shoes, which one would wear all day and might forget to remove when returning home; poorly adjusted glasses.	

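### The by-eye ocular symptom items on Form 3 are not repeated after heating, so non-pain symptoms have no standard comparison with baseline, least of all at Day 1

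*Combined protocol and SAP*

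**What the plan says.** Section 5.4.2 lists eyelid or eye pain, two kinds of irritation or inflammation, and nine ocular symptoms: "Burning, stinging, tearing, itching, discharge, redness, foreign body sensation, visual disturbance, sensitivity to light".

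Form 3 asks Yes/No, with a field for the eye, about symptoms that include "Mucus Discharge" and "Itchy/Burning", as well as redness, gritty feeling, tearing, glare and blurred vision. The table of required case report forms calls for Forms 1-5 before treatment, Forms 4-5 after treatment and Form 5 alone at follow-up, so Form 3 is completed once. Appendix 1 lists no later symptom checklist either.

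On what happens after heating, the visible text of Section 3.2 reads "Post-procedure, the subject shall report any discomfort to the study site". Appendix 1 schedules adverse events at treatment, post-treatment and the Day 1 follow-up, and Section 5.3 requires that every exposed subject be evaluated for them. The forms table then asks for "Form 8 with any Adverse Event". Form 8 has a free-text diagnosis, with no symptom list and no OD/OS field. Section 7.3 reports each type of event as a count and percentage of subjects.

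**The concern.** Adverse events and serious adverse events are the safety outcomes in Section 2.3, and Section 7.2 says the study is meant to support an initial safety determination. How symptoms are elicited after heating therefore matters. The plan records a by-eye symptom baseline and then does not use the same items again, so the natural before/after comparison is not available for most of the symptoms the sponsor itself expects.

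Day 1 matters most. Both eyes receive anesthetic drops before heating, which may blunt what subjects feel on Day 0, yet the only form required of everyone at Day 1 is a pain score. If non-pain symptoms are under-recorded, a low or zero percentage in the report would partly reflect how subjects were asked. There is no untreated eye to compare with, because both eyes are treated.

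**Working it through.** **The plan's own figure.** Section 7.2 gives 15 subjects and 30 eyes; 15 × 2 = 30, which agrees. No event rate, precision target, alpha or power is stated, so there is no sample-size calculation to reproduce. The check is a match of the Section 5.4.2 symptoms to the forms required at each visit.

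| Symptom (5.4.2) | Form 3, before treatment | Required forms, Day 0 after heating | Required form, Day 1 |
|---|---|---|---|
| Burning | "Itchy/Burning" | none specific | none specific |
| Stinging | none | none specific | none specific |
| Tearing | tearing | none specific | none specific |
| Itching | "Itchy/Burning" | none specific | none specific |
| Discharge | "Mucus Discharge" | slit lamp (Form 4) | none specific |
| Redness | redness | slit lamp (Form 4) | none specific |
| Foreign body sensation | gritty feeling | none specific | none specific |
| Visual disturbance | blurred vision | visual acuity (Form 4) | none specific |
| Light sensitivity | glare (close) | none specific | none specific |

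Counts:

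- Before treatment: 9 − 1 (stinging) = 8 of 9 have the same or a close item.
- Day 0 after heating: 9 − 3 = 6 of 9 have no specific item. The other 3 have an examination sign, not a question to the subject.
- Day 1: 0 of 9 have a specific item.
- Over all 12 entries in Section 5.4.2, the three others are covered on Day 0 (pain by Form 5, the two inflammation entries by Form 4). So 6 of 12 lack a specific item on Day 0. At Day 1 only pain has one, so 12 − 1 = 11 of 12 rest on the general adverse event evaluation.

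The matching involves judgment. If the slit-lamp tear film row were accepted as a counterpart for tearing, the Day 0 count would be 6 − 1 = 5 of 9. The Day 1 count would not change.

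**Illustration of what incomplete capture would do.** The documents give neither the true proportion of subjects with a symptom (p) nor the share of them that the adverse event evaluation picks up (s). Both are assumed here.

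- Expected reported percentage = p × s. With p = 3/15 = 20%: 20% × 0.30 = 6% and 20% × 0.70 = 14%.
- Chance of at least one report among 15 = 1 − (1 − p × s)^15:

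| p | s = 1 | s = 0.75 | s = 0.5 | s = 0.25 |
|---|---|---|---|---|
| 10% | 79% | 69% | 54% | 32% |
| 20% | 96% | 91% | 79% | 54% |

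- With 0 of 15 reported, the one-sided 95% upper bound on the reported rate is 1 − 0.05^(1/15) = 18.1%. Dividing by s gives the bound on the true rate: 18.1% at s = 1, about 24% at s = 0.75 and about 36% at s = 0.5.

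These figures show how the reading of a low count depends on capture. They do not estimate capture in this study.

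**The case against.** The strongest reply is that adverse events are actively assessed. Section 5.3 and Appendix 1 cover every exposed subject at three time points, Form 6 asks Yes/No about events during treatment, and Form 8 has a box for a subject with none. A reader might infer from Section 3.2 that symptoms come to light only if volunteered; the documents do not support that. What stands is narrower: the visible text gives no wording or method for the question, so elicitation is not standardized.

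A reader might also infer that nothing is asked by eye after heating. That is wrong for pain and discomfort, which Form 5 scores for each eye at all three times. Its anchors mention eye irritation and soap in the eye, so some burning or stinging may show in the score. Form 4 also repeats visual acuity, slit lamp, lid margin and staining by eye on Day 0. These are signs, however, and none is scheduled at Day 1.

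Nor is it true that a reported symptom cannot be classed as new: it can be looked up on the baseline Form 3. Worsening is the harder case, because Form 3 is Yes/No and Form 8 does not tie the event to an eye. How often baseline symptoms will occur is unknown; the study enrolls healthy eyes and excludes ocular surface and lid abnormalities.

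Finally, text is blacked out around Section 3.2 and the opening of Section 5. The point therefore rests mainly on Appendix 1, the required-forms table and Form 8, which are readable.

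**Conclusion.** The point holds as a gap in standardization. Eight of the 9 named symptoms have a baseline item. After heating, 6 of 9 have no specific item on Day 0, and none of the 9 has one at Day 1. New or worse non-pain symptoms therefore lack a standard by-eye comparison with baseline, and the Section 7.3 percentages may understate them.

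A firm statement that those percentages are biased towards zero would go too far. It requires that symptoms are in fact missed, and the documents give no capture rate; the percentages in the illustration rest wholly on assumed values. The counts assume the matching in the table and that the readable forms table and schedule are complete.

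The temperature objective is unaffected. This is a cheap improvement to the safety data and worth making before enrollment.

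**What to change.** - Widen Section 3.2 from discomfort to 'any new or worse eye or eyelid symptom'.
- Repeat only the Form 3 ocular items that match Section 5.4.2 (discharge, redness, gritty feeling, itchy/burning, tearing, glare, blurred vision), and add stinging at baseline and later. Ask by eye at Post-Treatment and, above all, at the Day 1 follow-up. Leave out history-type items such as haloes at night.
- Give each item a 'new / same / worse' tick. Repeating Yes/No alone would not detect worsening.
- On Day 0, ask before the fluorescein and Goldmann tests, and note in the report that anesthetic drops may blunt symptoms.
- Add the items to the required-forms table and to Appendix 1, and add an OD/OS field to Form 8.
- In Section 7.3, report the number and percentage of subjects with any new or worse solicited symptom separately from other adverse events.

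The cost is one or two minutes per contact, at contacts already scheduled, for at most 15 subjects. The downside is a higher count of solicited symptoms, some possibly caused by the eye tests; separate reporting keeps that visible.

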4 STUDY PROCEDURES

4.1 INFORMED CONSENT

Prior to recruitment of any subjects into the study, written approval of the protocol and informed consent form must be obtained from the Institutional Review Board (IRB).

Informed consent must be obtained and documented in writing prior to the initiation of any study procedures. The subject must be allowed sufficient time to thoroughly read the informed consent form, which will be written at a level that can be understood by someone educated to an 8th grade level. The Investigator or his/her designee should answer any questions that the patient might have. If the patient agrees to participate in the study, i.e., provides informed consent, the patient must sign both copies of the informed consent form. The witness and the Investigator or designee must also sign both copies of the informed consent form. One copy of the informed consent form shall be given to the subject/representative. If applicable, it shall be provided in a certified translation of the respective subject's language. The date of the subject's signature on the informed consent form shall be noted in the subject's medical chart.

Subjects who provide informed consent and with the consent documented in writing in their medical record may be screened for eligibility. Screened subjects' clinical identifiers shall be recorded on site-specific screening logs and once they are determined as being eligible, they may be enrolled into the study.

[figure not shown]
Individual patients may withdraw their consent to participate in the trial at any time. Also, an Investigator may discontinue a patient's participation in the trial at any time to protect the safety, rights, or welfare of the patient.

4.2 Assignment of Subject Identification

A subject identification number (ID) shall be assigned at screening. This ID shall be used on all study-related documents. To maintain confidentiality, the subject's name shall not be recorded on any study document other than the informed consent form.

4.3 SCHEDULE OF STUDY ASSESSMENTS

All procedures shall be performed according to the schedule in Appendix 1 unless otherwise specified.

5 SAFETY PARAMETERS

Safety assessments include adverse events/serious adverse events,

5.1 DEFINITION OF ADVERSE EVENTS

An adverse event is any untoward and unintended sign, symptom or disease temporally associated with the use of an investigational drug or device, or other protocol-imposed intervention, regardless of the suspected cause. Conditions or diseases that are chronic but stable should not be recorded on AE pages of the CRF. Changes in a chronic condition of disease that are consistent with natural disease progression are NOT adverse events and also should not be recorded on the AE pages of the CRF.

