5.3 ADVERSE EVENT ASSESSMENT AND DOCUMENTATION

All subjects who have been exposed to the study treatment shall be evaluated for adverse events. All adverse events, regardless of severity and whether or not they are ascribed to the study treatment, shall be recorded in the source documents and CRF using standard medical terminology.

All adverse events shall be evaluated beginning with onset, and evaluation shall continue until resolution is noted, or until the investigator determines that the subject's condition is stable. The investigator shall take appropriate and necessary therapeutic measures required for resolution of the adverse event. Any medication necessary for the treatment of an adverse event must be recorded on the adverse event case report form.

All AEs shall be characterized by the following criteria:

Page 32 of 65

- Event diagnosis
- Intensity or severity
- Expectedness
- Relatedness to study treatment
- Treatment or action taken.
- Outcome

Whenever possible, recognized medical terms should be used when recording AEs. Colloquialisms and/or abbreviations should not be used. Only one medical concept, preferably a diagnosis instead of individual symptoms, shall be recorded as the event.

If more than one distinct adverse event occurs, each event shall be recorded separately.

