7 STATISTICAL PLAN

No formal hypotheses will be used in this study. Subject demographic characteristics and background variables shall be summarized.

Pre-treatment, post-treatment and maximum treatment temperatures will be summarized with N, mean, standard deviation, minima, maxima, median, and interquartile range. The maximum change recorded will be similarly summarized.

All subjects enrolled and treated in the study shall be included as part of the safety analysis.

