APPENDIX 1: SCHEDULE OF ASSESSMENTS

[figure not shown]
	PRE-	TREATMENT	POST-	FOLLOW UP
ASSESSMENT	TREATMENT		TREATMENT	
Treatment Window	Day 0	Day 0	Day 0	Day 1 (-0/+3 davs)
Informed Consent	X			•
Demographics/medical/ocular history	X			
Visual Acuity	X		X	
Slit Lamp for Anterior Segment health	X		X	
Lid Margin Abnormalities	X		X	
Corneal fluorescein staining slit lamp evaluation	X		X	
Intraocular pressure	X		×	
Cornea and surrounding eye tissue temperature	X		X	
iLux heating		X		
Discomfort/pain questionnaire	X		X	X
Adverse Events		X	X	X

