Were you able to remove the disposable from the packaging and load the disposable into the device as instructed by the User's manual?	☐ Yes ☐ No		
Were you able to apply pressure to the eyelid without difficulty?	☐ Yes ☐ No		
Were you able to apply heat to the eyelid without difficulty?	☐ Yes ☐ No		
Were you able to view the eyelid margin with the magnifier without difficulty?	☐ Yes ☐ No		
Were you able to recharge the battery as described in the User's manual?	☐ Yes ☐ No		
For an answer of "No" above, please provide additional details below:			

FORM 8: ADVERSE EVENT- Page 1 of 1

Timepoint of adverse event:	☐ Treatment ☐ Post-Treatment ☐ Follow-Up☐ No Adverse Events for this Subject
Date adverse event began (DD-MMM-YYYY)	
Time adverse event began (24-hour format, HH:MM)	:
Was the event a serious adverse event (SAE)? If Yes, indicate which criteria meets the protocol definition of SAE Led to death Led to serious deterioration in the health of the patient that resulted in: - A life-threatening illness or injury - A permanent impairment of a body function - In-patient or prolonged hospitalization - Medical or surgical intervention to prevent life-threatening illness or injury or permanent impairment to body structure or a body function Was the event device-related? Was the event procedure-related? Was the event an unanticipated adverse event?	☐ Yes ☐ No ☐ Related ☐ Not Related ☐ Related ☐ Not Related ☐ Yes ☐ No
Event severity	☐ Mild ☐ Moderate ☐ Severe
Diagnosis of adverse event:	
Treatment or action taken to treat adverse event:	□ None □ OTC/Rx Drug □ Non-Drug Treatment/Procedure □ Hospitalization/ER Visit
Action taken during procedure:	☐ None ☐ Study Procedure Interrupted ☐ Study Procedure Discontinued
Outcome of event:	☐ Resolved without sequelae ☐ Resolved with sequelae (specify below) ☐ Ongoing ☐ Death ☐ Unknown
Date of resolution:	Time of resolution:: □ N/A
Briefly describe the event, including any sequelae:	
Investigator Signature:	Date:Page 52 of 65

SUBJECT ID:	_
-------------	---

FORM 9: DEVI	CE EXPERIENCE REPO	RT FORM- Page I of I
Date of event (DD-MMM-YYYY)		
Time of event (24-hour format, HH:MM)	:	-
Did the event result in an adverse event?	☐ Yes ☐ No	If Yes,please fill out an AE Form
Device(s) involved in the event (check all that apply):	☐ iLux Instrument ☐ iLux ☐ QC Checkor ☐ Magnifie	Disposable ☐ Batteries ☐ Charging Stand
	☐ Other, please specify:	

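### The adverse event definition covers any protocol-imposed intervention, but scheduled collection opens only at Treatment, so pre-treatment examination events have no proper place in the record or the tables

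*Combined protocol and SAP*

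**What the plan says.** Section 5.1 sets a wide definition: an adverse event is an untoward sign, symptom or disease "temporally associated with the use of an investigational drug or device, or other protocol-imposed intervention, regardless of the suspected cause". Conditions that are chronic and stable are excluded, but examination effects are not.

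Appendix 1 puts "Corneal fluorescein staining slit lamp evaluation" and intraocular pressure at both Pre-Treatment and Post-Treatment. Form 4, which is required at both visits, names Goldmann as the pressure method.

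The collection and analysis rules are narrower. Section 5.3 says "All subjects who have been exposed to the study treatment shall be evaluated for adverse events", and Section 7 says "All subjects enrolled and treated in the study shall be included as part of the safety analysis". The adverse event row in Appendix 1, and in its copy in the case report forms, is marked for Treatment, Post-Treatment and Follow-Up and is blank for Pre-Treatment. The list of required forms asks for Forms 1 to 5 at Pre-Treatment and brings in Form 8 from Treatment onward. On Form 8 the item "Timepoint of adverse event" offers those same three periods, plus a box for no events.

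Section 5.3 also contains wider language: "All adverse events, regardless of severity and whether or not they are ascribed to the study treatment, shall be recorded", and "All adverse events shall be evaluated beginning with onset, and evaluation shall continue until resolution is noted" or the condition is judged stable.

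**The concern.** The definition and the collection window do not start at the same place. The pre-treatment examination involves a dye and a tonometer in both eyes. An event that it causes is an adverse event under Section 5.1, yet a site working from the schedule and forms is not prompted to record it at the visit where it occurs.

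This matters because Section 2.3 lists adverse events and serious adverse events as the safety outcome measures, the study is non-randomized and open label with no control group described, and up to 15 subjects are planned. Without a comparator, the timing of onset and the investigator's judgement carry the attribution. Timing helps only if the record can show that an event began before the device was used. Ocular surface irritation or inflammation is an anticipated event in Section 5.4.2, so an examination effect and a device effect can look alike.

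**Working it through.** The plan gives no figure to reproduce on this point. The check is a cross-reading, followed by a small calculation for scale.

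**1. Where the window opens**

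| Place | What it covers |
|---|---|
| Section 5.1 | Device or any other protocol-imposed intervention |
| Appendix 1 and its copy in the forms | Treatment, Post-Treatment, Follow-Up; Pre-Treatment blank |
| Required-form list | Form 8 from Treatment onward; Pre-Treatment has Forms 1 to 5 |
| Form 8 timepoint boxes | Treatment, Post-Treatment, Follow-Up |
| Section 5.3, first sentence | Subjects exposed to study treatment |
| Section 7 | Subjects enrolled and treated |

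Both copies of the schedule row are legible and agree, so the gap does not come from missing or redacted text. Section 4.3 makes Appendix 1 govern unless otherwise specified.

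**2. A subject examined but not treated.** Suppose the pre-treatment examination causes a corneal event. The subject may then meet the exclusion for ocular surface abnormality (Section 2.4) or be withdrawn by the investigator for safety (Section 4.1). The first sentence of Section 5.3 does not call for evaluation, no Form 8 is scheduled, and Section 7 leaves the subject out. Forms 4 and 5 at Pre-Treatment record ocular status and pain, not adverse events. A serious event is still covered, because the 24-hour reporting rule in Section 5.5 is not limited to treated subjects. The gap therefore concerns non-serious events.

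**3. A subject examined and then treated.** Section 5.3 requires the event to be recorded whatever its cause. Form 8 takes the date and clock time of onset and has separate device and procedure items, each with a Not Related option. Four features still leave room for error:

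- The earliest timepoint box is Treatment, which is wrong for an event that began earlier.
- Form 6 records the procedure date and heating durations in seconds, but no clock time. Everything up to Post-Treatment is on Day 0, so the Form 8 onset time has nothing to be compared with.
- Section 5.3.3 judges relatedness against iLux heating. Not Related requires, among other things, that the event not fit a known response pattern, and Section 5.4.2 makes surface irritation an anticipated event.
- Section 7.3 tabulates subjects with each event and does not split by onset.

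**4. Scale.** Section 7.3 reports numbers and percentages of subjects. Assume all 15 planned subjects (Section 7.2) are treated. One event placed in the wrong period changes a rate by 1/15 = 6.7 percentage points. With exact (Clopper-Pearson) 95% limits:

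- 0/15 = 0%; upper limit 1 − 0.025^(1/15) = 21.8%.
- 1/15 = 6.7%; 0.2% to 31.9%.
- 2/15 = 13.3%; 1.7% to 40.5%.

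The documents give no frequency for examination-related events. The range 0 to 2 of 15 is assumed and shows scale only.

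**The case against.** A reader might infer that pre-treatment harm must either disappear or be charged to iLux. The documents do not support that. The recording sentence in Section 5.3 is not tied to attribution, Form 8 can carry an accurate onset time and a Not Related answer, and Section 5.5 captures serious events in anyone. Even for an untreated subject, the recording sentence in Section 5.3 pulls against the schedule, so it is safer to say that no record is scheduled than that none would ever be made.

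A reader might also infer that collection starts when the heat is switched on. It starts at the Treatment column, and Form 6 for that visit also covers preparation, including the anesthetic drops.

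Three further objections have force. Restricting the safety set to treated subjects is a coherent choice for a device summary and is not in itself an error. Fluorescein and tonometry are repeated Post-Treatment, inside the window, so a before-and-after split cannot isolate all examination effects. And no formal hypothesis or stated threshold depends on the event rate. The Pre-Treatment slit lamp, staining and pain entries also give a baseline, although they are not event records.

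What remains is that a site following the schedule and forms as written gives a pre-treatment event the wrong timepoint in a treated subject, and has no scheduled form for a non-serious one in an untreated subject.

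**Conclusion.** The mismatch is real and limited. The definition in Section 5.1 is wider than the collection window, and the schedule, its copy, the form list, Form 8, the first sentence of Section 5.3 and Section 7 all take the narrower view. For non-serious events in untreated subjects, the result is no scheduled record and no place in the analysis. For treated subjects, the result is a wrong period label and a raised chance of misattribution, which the onset time and relatedness items may or may not correct.

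The size is unknown. The shift of 6.7 percentage points per event assumes 15 treated subjects and says nothing about how often such events occur. No test or decision rule is affected. Priority is low to moderate: the consequence is modest, but it touches the listed safety outcome and is cheap to repair before enrolment.

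**What to change.** - **Appendix 1 and its copy in the forms:** mark Adverse Events at Pre-Treatment.
- **Form 8 and the required-form list:** list Form 8 for Pre-Treatment and add a Pre-Treatment box.
- **Section 5.3:** evaluate adverse events from the first protocol-imposed procedure, in all subjects who undergo one.
- **Form 6:** record the clock time at which the iLux pad is first placed. First heating is the wrong cut-point, because the pad is positioned and compression applied before the heat is activated (Section 3.1), and Section 5.4.1 notes that the disposable may touch the conjunctiva or cornea. A cut at heating would move harm from placement or compression out of the device period.
- **Section 7.3:** tabulate events with onset before that time separately from treatment-emergent events, and list events in untreated subjects.

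The safety set can stay as treated subjects for the device summary. The split does not replace investigator attribution, because the same examinations are repeated after treatment. Anesthetic drops precede pad placement in the Protocol Summary, so events from them would fall in the earlier group; Section 7.3 should say so.

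The cost is a schedule mark, a tick box, one new time field and a few sentences. The downside is that a few minor examination-related events may appear in the report.
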